2.2 Individual Treatment Period Visit Activities

This section presents a list of activities performed during the Treatment Period, organized by visit. The dot pattern depicted at the beginning indicates the place of the visit in the overall Treatment Period Activity Schedule. There are 10 dots representing the 10 visit types that are associated with the treatment Period beginning with Day 1 (Baseline), Month 1 to 6, Premature Discontinuation (PD), Product Collection Visit, and Unscheduled Visit (UNSCH).

Scheduled monthly visits during the Treatment Period are based on a 28-day month. Month 1 through 5 visits must occur within ± 5 days of the projected date. A -5 or +6 days visit window will be allowed in order to collect sanitary products from the last episode of menstrual bleeding or spotting prior to the Month 6 visit if menstrual bleeding starts immediately prior to or coincides with the scheduled visit. The subject will be instructed to continue taking study drug from the extra blister card until she returns for the Month 6 visit.

In the event that a subject or study personnel cannot come to the site because of the COVID-19 pandemic, study visits may be conducted over the phone where feasible, and AbbVie should be notified.

Activities are grouped by category (Interview, Exam, etc.). Further information about each activity is provided in Section 3.

Day 1 (BASELINE):

 INTERVIEW	
 • Eligibility criteria • Medical history (including tobacco and alcohol use) • Symptom-directed gynecological/obstetrical history 	
 • AE assessment • Prior/concomitant therapy • Physician Surgery Questionnaire (PSQ)
 EXAM	
 • Contraception counseling/dispense contraceptives as necessary • Birth control attestation • Vital signs 	
 • Symptom-directed physical exam • Dispense sanitary products collection kit (keg, collection bag, etc.) • Return sanitary products
 PRO	
 • Reason for Study Participation Questionnaire • C-SSRS Baseline/Screening 	
 • Uterine Fibroid Symptoms Quality of Life (UFS-QoL)
 LAB	
 • Urine pregnancy test (if positive, perform a serum pregnancy test) 	
 • Draw venous blood sample (if a keg is returned)

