## 8.4 Additional Efficacy Analyses

### MBL Volume

The change and percent change from Baseline to the Final Month in MBL volume obtained from the primary analysis after multiple imputation will be summarized by treatment group and compared between the elagolix treatment group and placebo, using one-way ANCOVA with treatment as the main effect and Baseline MBL volume as a covariate. Baseline and Final Month MBL volumes obtained for the primary analysis will be used.

The comparison of change or percent change from Baseline in MBL volume to each month between the elagolix treatment group and placebo will be performed using a Mixed Model Repeated Measures (MMRM) model with observed MBL volume, as described in [Section 8.2](#).

For the analysis above using observed MBL volume in each 28-day interval, only subjects who did not prematurely discontinue in or before this 28-day interval will be included. For example, for Study Days 29 – 56, it includes subjects who were on treatment for at least 56 days.

Plots will be provided by treatment group using the MBL volume data for the primary analysis (multiple imputation):

- Cumulative distribution function for MBL volume at Final Month;

- Cumulative distribution function for percent reduction from Baseline to Final Month in MBL volume;
- Cumulative distribution function for reduction from baseline to Final Month in MBL volume.

Plots will be provided by treatment group using observed MBL volume data:

- Mean change from Baseline in MBL volume over time.

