### **Amenorrhea**

The number and percentage of subjects who achieve amenorrhea will be calculated for each treatment group. The amenorrhea analysis includes subjects on study drug for at least 38 days. For each subject, amenorrhea at the Final Month is defined as having 0 days of bleeding or spotting during the last 28 days prior to and including the last dose day, with the interval starting at or beyond Study Day 11. If a subject does not have evaluable AH data during the last 28 days and no bleeding or spotting or "There was no visible blood on the sanitary products" is indicated on UBQ, then she is considered amenorrheic. The denominator will be the number of subjects with at least 38 days on study drug and having an amenorrhea status at the Final Month. The number and percentage of subjects with amenorrhea at Final Month will be summarized by treatment group and compared between the elagolix treatment group and placebo using the Miettinen-Nurminen (M-N) method.

Time to amenorrhea is defined as the number of days from the first study drug dose date to the day a subject achieves amenorrhea (i.e., the day a subject achieves amenorrhea – the first study drug dose date + 1). For a subject who achieves amenorrhea, the day she achieves amenorrhea is defined as the next day of the last bleeding/spotting day during the Treatment Period. The median, Q1, and Q3 of time to amenorrhea will be calculated for subjects who achieve amenorrhea using Kaplan-Meier method.

In the monthly analysis of bleeding for amenorrhea, the numerator will be the number of subjects on treatment who do not bleed or have spotting during the specified time window specified in [Table 1](#) (but may have begun bleeding or spotting thereafter) and the denominator will be the number of subjects on study drug for the full window and having an amenorrhea status for that month.

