**Table 1. Monthly Analysis of Bleeding for Amenorrhea**

Time Interval	Amenorrheic Status
Month 1 (Days 2 – 28)	Subject do not bleed or have spotting during Study Days 2 – 28 (Truncated, 27-day window)
Month 2 (Days 29 – 56)	Subject do not bleed or have spotting during Study Days 29 – 56
Month 3 (Days 57 – 84)	Subject do not bleed or have spotting during Study Days 57 – 84
Month 4 (Days 85 – 112)	Subject do not bleed or have spotting during Study Days 85 – 112
Month 5 (Days 113 – 140)	Subject do not bleed or have spotting during Study Days 113 – 140
Month 6 (Days 141 – 168)	Subject do not bleed or have spotting during Study Days 141 – 168
Final Month (last 28 days prior to and including the last dose day)	Subject do not bleed or have spotting during the last 28 days prior to and including the last dose day

Incidence and cumulative incidence of amenorrhea by last bleeding/spotting day at each month will be reported using the categories specified in [Table 2](#).

The summary will be provided including all subjects who have at least 38 days on study drug. If a subject meets the criteria for amenorrhea but discontinues, this subject's amenorrheic status will be carried forward to the time points after the subject has discontinued study drug. The denominator will be the number of subjects who have at least 38 days on study drug and have an amenorrhea status at Final Month.

Plots will be provided by treatment group for percentage of subjects with incidence and cumulative incidence of amenorrhea during the Treatment Period, respectively.

In all the analysis for amenorrhea above, if the observed MBL volume over a window (but treat "Subject only had spotting that did not require the use of sanitary products" on UBQ the same as bleeding) is 0 mL for a subject, then the subject is considered as no bleeding/spotting during that interval. Last bleeding/spotting day refers to the last day with observed AH data > 0 mL or the last day with UBQ indicating bleeding or spotting.

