### **Suppression of bleeding**

Suppression of bleeding is defined similarly to amenorrhea except that spotting is allowed. For each subject, achieving suppression of bleeding at the Final Month is defined as having 0 days of bleeding (spotting allowed) during the last 28 days prior to and including the last dose day with the interval starting at or beyond Study Day 11. The

suppression of bleeding analysis includes subjects with at least 38 days on study drug. If a subject does not have evaluable AH data during the last 28 days and no bleeding is indicated on UBQ ("Subject only had spotting that did not require the use of sanitary products" or "There was no visible blood on the sanitary products" is allowed), then the subject will be considered having achieved suppression of bleeding. The denominator will be the number of subjects with at least 38 days on study drug and having a suppression of bleeding status at the Final Month.

The number and percentage of subjects achieving suppression of bleeding at Final Month will be summarized by treatment group and compared between the elagolix treatment group and placebo using the Miettinen-Nurminen (M-N) method.

Time to suppression of bleeding is defined as the number of days from the first study drug dose date to the day a subject achieves suppression of bleeding (i.e., the day a subject achieves suppression of bleeding – the first study drug dose date + 1). For a subject who achieves suppression of bleeding, the day she achieves suppression of bleeding is defined as the next day of the last bleeding day during the Treatment Period. The median, Q1, and Q3 of time to suppression of bleeding will be calculated for subjects who achieve suppression of bleeding using Kaplan-Meier method.

Monthly analysis of bleeding for suppression of bleeding, incidence and cumulative incidence of suppression of bleeding will be provided in the same way as will be done for amenorrhea in [Table 1](#) and [Table 2](#). Plots will be provided by treatment group for percentage of subjects with incidence and cumulative incidence of suppression of bleeding during the Treatment Period, respectively.

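### The Month 6 rows of the monthly amenorrhea and suppression-of-bleeding analyses (SAP 8.4) can drop women who completed treatment, because they require dosing through Day 168 while the Month 6 visit, where dosing ends, may fall earlier

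*SAP*

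**What the plan says.** **Denominator.** SAP 8.4 (Amenorrhea) states for the monthly analysis that "the denominator will be the number of subjects on study drug for the full window and having an amenorrhea status for that month". The Month 6 row of SAP Table 1 reads "Subject do not bleed or have spotting during Study Days 141 – 168". For suppression of bleeding, the monthly analysis "will be provided in the same way as will be done for amenorrhea".

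**Visit timing.** Protocol Operations Manual 2.2 states: "Scheduled monthly visits during the Treatment Period are based on a 28-day month". For Month 6 it adds "A -5 or +6 days visit window will be allowed in order to collect sanitary products from the last episode of menstrual bleeding or spotting", with the condition "if menstrual bleeding starts immediately prior to or coincides with the scheduled visit". A woman waiting for a delayed visit keeps dosing from her spare blister card until she attends. The Month 6 visit list has drug accountability but no dispensing, so for a completer the Month 6 visit is where dosing stops.

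**Monthly MBL.** SAP 8.4 (MBL Volume) gives a rule and an example. The rule removes only women who discontinued prematurely in or before the interval. The example says "For example, for Study Days 29 – 56, it includes subjects who were on treatment for at least 56 days".

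**Final Month.** SAP 8.1 anchors Final Month on the last dose day, not on Day 168.

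**The concern.** The monthly rule ties inclusion to a fixed study day, but a completer's last dose is set by a visit date that the protocol allows to move. At Months 1–5 this does no harm, because a woman who continues in the study is still dosing when the window closes. At Month 6 a woman can attend on an allowed day, complete treatment, and still not be on drug on Day 168. No SAP text keeps her in the Month 6 row.

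The visit shift is allowed because of bleeding near the scheduled date, and bleeding is what amenorrhea and suppression measure. Inclusion at Month 6 therefore depends partly on the outcome. Month 6 is the last monthly time point for two listed efficacy endpoints, and the arms are small: 32 and 16 randomized. One placebo woman is 1/16, about 6%, of her arm.

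**Working it through.** **Inputs.** 28-day month, and a Month 6 window of −5 to +6 days (Operations Manual 2.2). Month 6 is Days 141–168 (SAP Table 1). The documents do not say whether the projected Month 6 date is Day 168 or Day 169, or whether a dose is taken on the visit day, so all four combinations are shown.

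**The plan's own window.** 5 × 28 + 1 = 141 and 6 × 28 = 168, which reproduces Table 1. The sample size plays no part in this check.

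**Last dose day.** L = target + visit offset − lag, where lag is 0 if she doses on the visit day and 1 if her last dose is the day before. She meets the Month 6 denominator only if L ≥ 168.

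| Target | Lag | L at −5 | Window days covered (L − 140) | Days short (168 − L) | L if on time | Offsets (of 12) with L < 168 |
|---|---|---|---|---|---|---|
| 168 | 0 | 163 | 23 | 5 | 168 | 5 |
| 168 | 1 | 162 | 22 | 6 | 167 | 6 |
| 169 | 0 | 164 | 24 | 4 | 169 | 4 |
| 169 | 1 | 163 | 23 | 5 | 168 | 5 |

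At the earliest allowed visit every combination fails, by 4 to 6 days. In the second row even an on-time visit fails, by one day. The last column counts allowed days; it is not an estimate of the share of women affected.

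**Direction.** Two mechanisms consistent with the text pull opposite ways.
- If bleeding brings the visit forward, the women lost are bleeders and the amenorrhea rate rises.
- If bleeding mainly delays the visit, bleeders have L ≥ 168 and stay. Under the second row, non-bleeders seen on time are then lost and the rate falls.

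Illustration with assumed counts:
- 28 elagolix completers, 10 amenorrheic: 10/28 = 35.7%. Losing two bleeders gives 10/26 = 38.5%; losing two amenorrheic women gives 8/26 = 30.8%.
- 14 placebo completers, 1 amenorrheic: 1/14 = 7.1%. Losing two bleeders gives 1/12 = 8.3%; losing the one amenorrheic woman gives 0/13 = 0%.

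**What is not touched.** The primary endpoint and the Final Month amenorrhea, suppression and MBL analyses follow the last dose day, so an early finish does not remove her. The SAP Table 2 summaries need 38 days on drug and a Final Month status, not a fully treated month.

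**The case against.** **The early visit is not a general licence.** The Month 6 window is conditional on bleeding near the scheduled date. This stands. A reader might infer from the 4 to 6 of 12 allowed days that a third to a half of completers are lost. The documents do not support that: they give no distribution of visit dates and no completion rate, and the window is not open to every woman.

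**MBL is not clearly affected.** A reader might extend the Days 29–56 example to Month 6 and conclude that the repeated-measures MBL analysis also requires 168 days. The operative rule removes only premature discontinuers, which keeps an early completer. The example illustrates an interval in which nobody can yet have completed. Rule and example disagree for her, so this is an ambiguity and not a requirement.

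**The full-window rule has a purpose.** Product collection ends with the Treatment Period (Operations Manual 3.22), so days between an early last visit and Day 168 are unmeasured, and the rule avoids calling unmeasured days free of bleeding. This stands as a reason not to simply drop the requirement. It is no reason to discard a completer who has a 28-day interval ending on her last dose.

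**The consequence is small.** The Final Month comparisons carry the named test (Miettinen-Nurminen), the monthly rows name none, and Protocol Appendix E describes the study as exploratory. This stands and limits the weight of the point.

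**Conclusion.** The point holds for the Month 6 rows of the monthly amenorrhea and suppression analyses. As written, a protocol-compliant completer whose last dose falls before Day 168 is excluded. At the earliest allowed visit her last dose is on Day 162 to 164, and under one reading of the schedule an on-time visit also fails. The exclusion is linked to bleeding and so to the outcome.

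A bias in one particular direction is tempting to infer, but the condition on bleeding covers both the early and the late side of the window, so the text does not settle it. Nor can a headcount be given. The percentages in the illustration rest on assumed counts and show only that a few women matter in arms of this size.

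The result rests on dosing stopping at the Month 6 visit and on reading the denominator literally. It is worth correcting before the analysis, but it is confined to the last monthly row of two additional endpoints.

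**What to change.** **Amenorrhea and suppression, Month 6 row (SAP 8.4, Table 1 and the matching suppression text).** State that women who completed the Treatment Period are included, given a bleeding status. If the last dose is on or after Day 168, use Days 141–168 as now. If it is earlier, use the 28 days ending on the last dose day, which the SAP already derives as Final Month. Keep the full-window rule for premature discontinuers. Footnote the number of completers handled this way in each arm.

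**Monthly observed MBL (SAP 8.4, MBL Volume).** Reconcile the rule and the example by stating that treatment completers with observed Month 6 MBL stay in at Month 6. Leave Days 141–168 unchanged in the repeated-measures model and in the imputation of SAP 8.2. A shifted window there would overlap Month 5, so the same blood loss could count at two time points, and it would conflict with the fixed Month 6 used for imputation.

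**Cost.** SAP wording and one derivation; no new data. The derivation uses the recorded last dose date, so the Day 168 or 169 question need not be settled for it. For a woman with last dose on Day L, the interval starts on Day L − 27 and overlaps Month 5 by 140 − (L − 27) + 1 = 168 − L days, that is 4 to 6 days at the extreme. Her Month 6 and Final Month results are then identical, which the table should note.

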**Table 1. Monthly Analysis of Bleeding for Amenorrhea**

Time Interval	Amenorrheic Status
Month 1 (Days 2 – 28)	Subject do not bleed or have spotting during Study Days 2 – 28 (Truncated, 27-day window)
Month 2 (Days 29 – 56)	Subject do not bleed or have spotting during Study Days 29 – 56
Month 3 (Days 57 – 84)	Subject do not bleed or have spotting during Study Days 57 – 84
Month 4 (Days 85 – 112)	Subject do not bleed or have spotting during Study Days 85 – 112
Month 5 (Days 113 – 140)	Subject do not bleed or have spotting during Study Days 113 – 140
Month 6 (Days 141 – 168)	Subject do not bleed or have spotting during Study Days 141 – 168
Final Month (last 28 days prior to and including the last dose day)	Subject do not bleed or have spotting during the last 28 days prior to and including the last dose day

Incidence and cumulative incidence of amenorrhea by last bleeding/spotting day at each month will be reported using the categories specified in [Table 2](#).

The summary will be provided including all subjects who have at least 38 days on study drug. If a subject meets the criteria for amenorrhea but discontinues, this subject's amenorrheic status will be carried forward to the time points after the subject has discontinued study drug. The denominator will be the number of subjects who have at least 38 days on study drug and have an amenorrhea status at Final Month.

Plots will be provided by treatment group for percentage of subjects with incidence and cumulative incidence of amenorrhea during the Treatment Period, respectively.

In all the analysis for amenorrhea above, if the observed MBL volume over a window (but treat "Subject only had spotting that did not require the use of sanitary products" on UBQ the same as bleeding) is 0 mL for a subject, then the subject is considered as no bleeding/spotting during that interval. Last bleeding/spotting day refers to the last day with observed AH data > 0 mL or the last day with UBQ indicating bleeding or spotting.

**Table 2. Categorical Summary of Incidence and Cumulative Incidence of Amenorrhea**

Analysis	Time Interval	Numerator Calculation
Incidence	Month 2 (≤ Study Day 56)	Last bleeding/spotting day occurs during Study Days 1 – 28
	Month 3 (Study Day 57 – 84)	Last bleeding/spotting day occurs during Study Days 29 – 56
	Month 4 (Study Day 85 – 112)	Last bleeding/spotting day occurs during Study Days 57 – 84
	Month 5 (Study Day 113 – 140)	Last bleeding/spotting day occurs during Study Days 85 – 112
	Month 6 and after (Study Day ≥ 141)	Last bleeding/spotting day occurs after Study Day 113
Cumulative	Month 2 (≤ Study Day 56)	Last bleeding/spotting day occurs before Study Day 29
	Month 3 (Study Day 57 – 84)	Last bleeding/spotting day occurs before Study Day 57
	Month 4 (Study Day 85 – 112)	Last bleeding/spotting day occurs before Study Day 85
	Month 5 (Study Day 113 – 140)	Last bleeding/spotting day occurs before Study Day 113
	Month 6 and after (Study Day ≥ 141)	Last bleeding/spotting day occurs after Study Day 113

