 CENTRAL LAB	
 • Central laboratory tests (hematology, chemistry, lipid panels, urinalysis) • Pharmacodynamic sample (serum estradiol) (predose only) 	
 • Optional biomarker sample: whole blood (deoxyribonucleic acid [DNA]/ribonucleic acid [RNA]/serum/plasma)
 TREATMENT	
 • Randomization/drug assignment 	
 • Dispense study drug (the first dose should be administered at the site)

NOTES: The Baseline visit should occur on Days 1 through 10 of the start of menses (defined as the first day of menstrual flow).
 If urine pregnancy test is positive study drug must not be dispensed
 If urine pregnancy test is positive and confirmed by a positive serum pregnancy test, subject should be screen failed.

MONTH 1:

INTERVIEW	
 • AE assessment • Prior/concomitant therapy 	
EXAM	
 • Contraception counseling/dispense contraceptives as necessary • Vital signs 	
 • Dispense sanitary products collection kit (keg, collection bag, etc.) and remind subject to continue collection of sanitary products • Return sanitary products
PRO	
 • C-SSRS Since Last Visit • Uterine Bleeding Questionnaire (UBQ) (if no sanitary product is returned) 	
 • Patient Global Impression of Change – Menstrual Bleeding (PGIC-MB)
LAB	
 • Urine pregnancy test (if positive, perform a serum pregnancy test) 	
 • Draw venous blood sample (if a keg is returned)
TREATMENT	
 • Dispense study drug 	
 • Drug accountability

NOTES: One month = 28 days.

MONTH 2:

INTERVIEW	
 • AE assessment • Prior/concomitant therapy 	
EXAM	
 • Contraception counseling/dispense contraceptives as necessary • Vital signs 	
 • Dispense sanitary products collection kit (keg, collection bag, etc.) and remind subject to continue collection of sanitary products • Return sanitary products
PRO	
 • C-SSRS Since Last Visit • UBQ (if no sanitary product is returned) 	
 • PGIC-MB

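### SAP 8.4 Table 2 puts a woman with no bleeding on or after Study Day 1 in the denominator but in no incidence row, and her time to amenorrhea or suppression is undefined

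*SAP*

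**What the plan says.** All the rules are in SAP Section 8.4, apart from the timing of the first dose and the collection of sanitary products.

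- **Month 2 incidence (Table 2):** "Last bleeding/spotting day occurs during Study Days 1 – 28". The later incidence rows use later windows.
- **Month 2 cumulative incidence (Table 2):** "Last bleeding/spotting day occurs before Study Day 29", with no lower bound.
- **Table 2 denominator (text under Table 1):** "The denominator will be the number of subjects who have at least 38 days on study drug and have an amenorrhea status at Final Month".
- **Last bleeding day (text under Table 1):** "Last bleeding/spotting day refers to the last day with observed AH data > 0 mL or the last day with UBQ indicating bleeding or spotting". This sentence is not limited to the Treatment Period.
- **Time to amenorrhea:** for an achiever, "the day she achieves amenorrhea is defined as the next day of the last bleeding/spotting day during the Treatment Period". The median and quartiles are calculated among achievers.
- **Suppression of bleeding:** the day of achievement "is defined as the next day of the last bleeding day during the Treatment Period". The incidence summaries follow Tables 1 and 2, and a day counts as bleeding only above 2 mL or if the bleeding questionnaire (UBQ) says so.
- **Timing of the first dose (Operations Manual 2.2, Day 1 notes):** "The Baseline visit should occur on Days 1 through 10 of the start of menses".
- **Product collection (Operations Manual 3.22):** continuous from the first Screening cycle to the end of treatment.

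No rule covers a woman with no bleeding on or after Study Day 1.

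**The concern.** Because Day 1 may fall as late as the tenth day of menses, the baseline menses can be over before the first dose. A woman in that position who never bleeds again is the earliest possible achiever of amenorrhea. She qualifies at the Final Month and, with 38 days on drug, enters the Table 2 denominator. The Month 2 incidence numerator starts at Study Day 1, so it cannot count her, and the time rule gives her no value.

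What is at stake is the accuracy of the Month 2 incidence row, its agreement with the cumulative row beside it, and the median time to amenorrhea or suppression. The omission is one-directional because it removes early achievers. If elagolix works, they would be expected mostly in that arm. With about 48 women, a few cases would visibly move these tables and the plots drawn from them. The gap also leaves a choice to be made during programming.

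**Working it through.** The plan states no figure for this point, so the check applies its rules literally.

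**Inputs.** Table 2 row definitions, the Table 2 denominator, the last-bleeding-day definition and the time formula come from SAP 8.4. The formula is day of achievement minus first dose date plus 1. Arm sizes of 32 and 16 come from SAP 2.4.

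**Step 1: classify by last bleeding day.**

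| Last bleeding day | Incidence row | Cumulative rows | Time (days) |
|---|---|---|---|
| None on record (pre-dose days not used) | none | none | undefined |
| Study Day -3 (pre-dose days used) | none | Months 2 to 5 | undefined |
| Study Day 1 | Month 2 | Months 2 to 5 | 2 |
| Study Day 28 | Month 2 | Months 2 to 5 | 29 |
| Study Day 29 | Month 3 | Months 3 to 5 | 30 |

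The first two lines are the same woman under two readings of the last-bleeding-day sentence. On either reading she is missing from Month 2 incidence. A woman who bleeds on Study Day 1 and never again is counted, so the gap concerns only women with no bleeding from Study Day 1 onward.

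**Step 2: internal consistency.** Nothing precedes the first row, so Month 2 incidence and Month 2 cumulative incidence should be the same number. On the second line, cumulative exceeds incidence by one woman for each such case.

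**Step 3: time to achievement.** The rule requires a last bleeding day within the Treatment Period, and she has none. If a programmer used the pre-dose bleed anyway, a last bleed three days before the first dose would put achievement two days before it, and the formula would return -2 + 1 = -1 day. The shortest time the rule can validly produce is 2 days.

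**Step 4: size per woman.** Loss in Month 2 incidence = k/n, where k is the number of such women.
- n = 32: 1/32 = 3.1 points each. An assumed range of k = 1 to 4 gives 3.1 to 12.5 points.
- n = 16: 1/16 = 6.25 points each.

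The actual denominators can be smaller than 32 and 16, because they require 38 days on drug and a Final Month status. Each woman would then weigh slightly more.

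**Step 5: effect on a median, with invented data.** Take ten achievers with times 12, 20, 33, 36, 40, 62, 65, 70, 90 and 95 days, plus two who never bleed on treatment. Omitting the two gives (40 + 62)/2 = 51 days. Including them at 1 day gives (36 + 38 + 2)/2, that is (36 + 40)/2 = 38 days. This shows direction only.

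**Step 6: suppression.** A woman with no day above 0 mL also has no day above 2 mL. The affected group for suppression is therefore at least as large as for amenorrhea, and it also includes women whose only on-treatment blood loss was light.

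**The case against.** The strongest reply is that this is loose wording on a supplementary table and that the intention is clear. Table 2 labels the Month 2 interval with an upper limit only, and its cumulative row has no lower limit, so the authors probably meant to count these women. The endpoints listed in the protocol and SAP are the proportions with amenorrhea and suppression at the Final Month and at each month. Those come from the Final Month definition and Table 1, neither of which needs a last bleeding day, and both classify her correctly. Table 2 and the time summaries carry no specified test, and the protocol's summary of changes calls the study exploratory.

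Most of that stands, and it limits the reach of the point. It does not remove the defect: the incidence numerator as written excludes her whatever was intended, and the time rule has no value to give her.

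Several stronger readings are tempting, and the documents do not support them.

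- *These women have no last bleeding day at all.* This is certain only for the time rule. The general definition has no Treatment Period limit and collection starts in Screening, so a pre-dose bleed can serve.
- *The plan directs that they be dropped.* It does not; it is silent on them.
- *They are kept in every denominator.* This holds for Table 2. The Kaplan-Meier summary is of achievers, so there she is an achiever without a time.
- *A large share of achievers is lost.* If Day 1 visits were spread evenly over menses Days 1 to 10, menses of 5 to 8 days would be over before dosing in 50% to 20% of women. Neither the even spread nor the menses length is in the documents. The percentage would also apply only to women who never bleed again after the baseline menses, whose number is unknown.

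Table 2 has a separate fault: its last cumulative row counts last bleeding days later than Day 113, and Day 113 itself fits no row. That is independent of this point.

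**Conclusion.** The point holds in a limited form. For the Month 2 incidence row, the stated rule gives a figure that is too low by 1/n for each achiever with no bleeding on or after Study Day 1: 3.1 points at n = 32 and 6.25 points at n = 16. For the cumulative rows, the outcome depends on whether pre-dose days are used, which the SAP does not settle. For time to amenorrhea and time to suppression, her value is undefined although she belongs in the summary.

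The size in this trial cannot be stated, because the documents do not give the number of such women. A larger loss on elagolix is a reasonable expectation if the drug works, but the documents do not establish it. A reader might infer that the amenorrhea results as a whole, or the primary result, are biased. They are not: the primary endpoint, the Final Month proportions and the Table 1 monthly proportions are unaffected. The effect is confined to descriptive summaries and plots.

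**What to change.** Make two changes in SAP 8.4 before unblinding.

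1. Reword the Month 2 incidence row of Table 2: *last bleeding/spotting day on or before Study Day 28, or no bleeding/spotting on or after Study Day 1*. State that women with no bleeding/spotting on or after Study Day 1 are also counted in all cumulative rows. Carry the same wording to suppression, with bleeding in place of bleeding/spotting.
2. Add to both time rules: *a subject who achieves amenorrhea (suppression) and has no bleeding/spotting (bleeding) on or after Study Day 1 is assigned Study Day 1 as the day of achievement, giving a time of 1 day.*

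Both are needed, since rewording the row alone leaves the time undefined. Do not assign a last bleeding day of Study Day 1 instead: that would give a time of 2 days, the same as for a woman who did bleed on Day 1, and would record bleeding that did not occur. The cost is two short text edits and one added derivation rule.
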